5.1 Selection of Sites & Clinicians

Criteria for the selection of centres includes

- NHS Hospitals in the UK providing paediatric intensive care
- Historic high case load of bronchiolitis, as reported to PICANet
- Sufficient research capacity comprised of staff, time and facilities to undertake the trial; including patient screening and recruitment, randomisation, collection and provision to the CTRC of all required data, collection of research samples, identification and management of adverse events including notification to CTRC within protocol defined timeframes, identification and provision of information to the CTRC of all protocol breaches.
- All staff contributing to the trial must have valid certified Good Clinical Practice (GCP) training throughout the conduct of the trial. Requirements of the Sponsor are that renewal of GCP must occur every 3 years.
- Willingness to participate

Final decisions on site selection will be determined by the Trial Management Group (TMG) and will be described in the supplementary document 'BESS Site Suitability Assessment. Initiation of centres will be undertaken in compliance with CTRC SOPs². Centres fulfilling the criteria will be selected to be recruitment centres for the BESS trial and will be opened to recruitment upon successful completion of all global (e.g. MREC and MHRA) and study-specific conditions (e.g. site personnel training requirements) and once all necessary documents have been returned to CTRC as detailed in the trial Green Light checklist.

Participating centres will be listed in the 'BESS Participating Centres' log, maintained separately to the protocol and stored in the Trial Master File (TMF).

² CTRC SOP TM017 Study Initiation in CTRC and TM018 Study Initiation at Sites

IRAS 220853 Page **27** of **87**

6 STUDY POPULATION

6.1 Inclusion Criteria

- Term-born infants < 26 weeks old and preterm-born infants < 26 weeks corrected age[†]
- 2. Diagnosis of bronchiolitis (see below)
- 3. Requires conventional invasive MV via tracheal intubation
- 4. Parent or person with parental responsibility has given written informed consent for trial participation

Note: Infants with chronic lung disease of prematurity can be included in the trial.

† Correcting for prematurity is a well-established method for adjusting assessment of infants born prematurely who are anatomically, physiologically, immunologically and neuro-developmentally immature for their chronological age. In our study, term-born infants will be eligible for inclusion in the study up to chronological age of 26 weeks old (i.e. all those under 6 months old). Premature born infants have their age corrected to account for weeks of lost gestation, hence an infant born 12 weeks premature (i.e. before completing the 28th week of the 40 weeks of pregnancy) would still be eligible up to a chronological age of 38 weeks old (i.e. under 9 months), because that infant is still less than 26 weeks old when age is corrected for the premature birth.

6.1.1 Definition of bronchiolitis

Diagnosis of bronchiolitis will be made using clinical criteria defined in national guidance NICE-NG9 (17).

6.2 Exclusion Criteria

- 1. Major congenital anomalies
- 2. Congenital neuromuscular disease
- 3. Already intubated for MV for >48 hours or likely to have been intubated for MV for >48 hours by randomisation
- 4. Have received or are receiving extracorporeal membrane oxygenation (ECMO) or oscillation during this episode of bronchiolitis
- 5. Have received or are receiving intratracheal administration of any surfactant during this episode of bronchiolitis
- 6. Receiving MV for primary apnoea rather than respiratory failure
- A known hypersensitivity to the active substance or excipients of poractant alpha (Curosurf®)
- 8. A decision to wean to extubation has already been made
- 9. Clinical judgement of futility

IRAS 220853 Page **28** of **87**

6.3 Co-enrolment Guidelines

The investigators are happy to enter in to co-enrolment agreements where feasible. Where other trials are taking place at a site participating in BESS and the target population overlaps, sites should make the BESS team aware at the earliest opportunity so that the potential for co-enrolment can be discussed between the two trial teams. The BESS investigators are open to co-enrolment with other studies but this must be agreed between both Chief Investigators prior to randomisation into BESS.

IRAS 220853 Page **29** of **87**

7 RECRUITMENT AND RANDOMISATION

7.1 Participant Identification and Screening

All patients admitted to recruiting PICUs, receiving conventional MV for bronchiolitis, age <26 weeks (corrected for prematurity) will be screened for eligibility before trial entry. Screening and confirmation of full eligibility will be completed to allow randomisation within 48 hours of intubation.

A screening log of patients who are assessed for eligibility but not randomised will be maintained and returned to the CTRC on a regular basis, as this will provide important information for monitoring purposes. The screening log will capture which patients have been screened for the trial but assessed as ineligible, and those considered eligible and approached for consent but for whom consent was not obtained; reasons (all per subject) for non-inclusion will be recorded. Reasons for declining to participate will be asked routinely but it will be made clear that parents/persons with parental responsibility do not have to provide a reason unless happy to do so.

The screening log will not contain patient identifiers as those who are not eligible will not have provided their consent for identifiers to be captured as part of the trial. Therefore, sites will maintain their own trial register linking patients screening and/or randomisation numbers to their identifiers. Under no circumstances will this log be returned to the CTRC.

Patients will be reviewed for eligibility once they have been intubated for MV, or as soon as their arrival into PICU if they are already intubated. Parents/persons with parental responsibility for patients who meet the eligibility criteria and are suitable for inclusion (see 6.1 and 6.2) will be provided with information about the trial (both verbal and written) to consider participation.

Only a medically qualified doctor authorised on the site Delegation Log can confirm full eligibility of any patient. A record of this confirmation must be made in the patient's medical notes on the date of confirmation of eligibility.

7.2 Informed Consent

7.2.1 Prospective Informed Consent Process

Parents and those persons with parental responsibility may give consent for the patient to take part in BESS; hereafter throughout this protocol they shall be referred to as 'parent(s)'. Initiation of the intervention in BESS is urgent and the condition "critical illness due to bronchiolitis requiring MV" is a medical emergency. Randomisation must be completed within 48 hours of intubation for MV, which will limit the time available for a parent to consider whether or not their child should participate. Site research teams will use their understanding of the clinical situation for each individual patient to judge when is most appropriate to approach parents about trial participation. The trial concept will be introduced to a parent by familiar members of the usual clinical care team, be they nurses or physicians, as per the Canadian Critical Care Trials PICU Research Group trial recruitment model (24).

If a parent is interested, a member of the usual clinical care team will make an introduction to the research staff who will provide written study information and offer further verbal information.

IRAS 220853 Page **30** of **87**

Due to the time-critical nature of the intervention, the parent will have a limited timeframe to ask questions and make a decision about their child's participation in the trial. Randomisation must take place within 48 hours of intubation for MV and while some parents may have this full timeframe to consider trial participation, others may have considerably less due to time of arrival on PICU, time of approach etc. Consent will be sought by any appropriately trained and delegated medical staff and where local site policy allows, research nurses or respiratory physiotherapists (the research team).

Consent from the parent must be obtained prior to every infant participating in the trial. This consent will be sought after a full explanation has been given of the treatment options; including the conventional and generally accepted methods of treatment, the objectives, risks and inconveniences of the trial, and the conditions under which it is to be conducted.

Parent Information Sheet and Consent (PISC) forms, describing in detail the trial intervention, procedures and risks will be approved by a research ethics committee (REC). The parent will be asked to read and review this document. Upon reviewing the document, the person seeking consent will explain the research study to the parent. This information, and the supporting conversation, will emphasise that participation in the trial is voluntary and that the parent may withdraw their infant from the trial at any time and for any reason.

The parent will be given opportunity to ask any questions that may arise and time to consider the information, within the constraints of the 48 hour period between intubation and randomisation, prior to agreeing to participate. A contact point where further information about the trial may be obtained will be provided on the parent information sheet.

The parent will then sign and date the consent form if they agree to their infant participating. Both the person obtaining consent and the parent must sign and date the consent form; the researcher and parent must sign at the same time, with the researcher completing their signature **after** the parent.

A copy of the signed PISC will be given to the parent for their record. The original copy will be filed in the Investigator Site File, a copy filed in the participant's medical notes and a further copy should be sent to the CTRC. If the site has moved to an electronic health record (EHR), a scanned copy should be entered in the patient notes. A record of the consent process should also be recorded in the participant's medical notes.

The right of the parent to refuse consent for the infant to participate in the trial without giving reasons must be respected. After the infant has entered the trial, the clinician will remain free to give alternative treatment to that specified in the protocol, at any stage, if s/he feels it to be in the best interest of the patient. However, the reason for doing so should be recorded and the infant will remain within the trial for the purpose of follow-up and data analysis.

Similarly, the parent of the infant remains free to withdraw the infant at any time from the protocol treatment and trial follow-up without giving reasons and without prejudicing the further treatment of the infant (see section 8.6.2 for further details). They do not need to provide a reason for withdrawing their infant from the trial, which will be emphasised in the PISC. Any parent who withdraws their infant from the trial will be approached for participation in the sub-study of parental experience (WP-B), unless they previously declined sub-study participation at consent (see Section 12).

IRAS 220853 Page **31** of **87**

7.2.2 Consent for additional work

Parents of eligible infants who have been approached to give consent for the BESS trial will also be offered the opportunity to take part in a telephone interview about their experiences of the consent process. This will be offered regardless of whether or not consent was given for the infant to participate in BESS (see section12.1).

An alternative PISC will be offered to parents at Liverpool and Southampton PICUs (sites participating in the Mechanistic work exploring surfactant metabolism; WP-C. See section 12.2).

A decision to decline to participate in either WP-B or WP-C will not impact upon care, or preclude involvement in the trial (WP-A).

7.3 Randomisation Procedure

Participants will be randomised in a 1:1 ratio, stratified by site and duration of ventilation prior to randomisation (<24hrs, ≥24hrs).

Randomisation must be completed within 48 hours of intubation.

Participants will be randomised using a secure 24-hour web-based randomisation and drug supply programme, managed by a third party subcontracted by Chiesi Farmaceutici S.p.A. (Chiesi). A personal login username and password will be required to access the randomisation system. Designated research staff will be issued with a unique personal login and password upon completion of training in the use of the system.

When the system requirements (confirmation of consent and eligibility) are confirmed the participant treatment allocation and a unique study number (randomisation number) will be displayed on a secure webpage. The randomising staff member must select the partially completed unblinding envelope corresponding to the participant's randomisation number (as clearly displayed on the front of the envelope) and record the allocation on the printed slip inside. The unblinding envelope must then be sealed and transferred to an agreed secure location accessible to PICU staff.

Once a randomisation number has been generated, the randomising staff member will be able to enter the resupply module within the system, where they will select the participant weight category and dose number (i.e. first, second or third) for the system to allocate the required number of vials for the participant.

Sites must complete this step for participants in both arms of the trial and for every given dose (first, second or third) regardless of allocation to drug or placebo.

The randomisation and resupply system is configured to allow remote monitoring of stock levels at site by the distributor contracted by Chiesi, and further IMP stocks will be supplied once the amount available at site reaches an agreed trigger level. However, it remains the responsibility of the PI or delegated research staff to check the supplies available on the PICU prior to randomisation to ensure there is sufficient supply of the IMP, as the majority of stock will be held at the local site Pharmacy (see Section 9.2.6 for further information regarding intervention accountability).

IRAS 220853 Page **32** of **87**

Unblinded and appropriately delegated site staff will be able to log into the randomisation and resupply system at any time and view the allocations of each participant to ensure continuity between shifts.

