7.4 Blinding to Allocations

BESS will use an established strategy of a sham-procedure to blind as many research and usual care staff as possible to the nature of the intervention. This sham procedure was used in the development of surfactant as a therapy for surfactant deficiency of prematurity (6,19).

The participants, CTRC staff (excluding statistical team members as appropriate), and all members of the site research teams (excluding agreed randomising staff member, the administrator of the intervention and the dosage witness) will be blinded to treatment allocations. Occasional transient adverse effects associated with surfactant administration and back-tracking of surfactant up the endotracheal tube, plus the more frequently observed positive effects of rapid improvement in gas exchange immediately following surfactant administration, may result in some blinded care givers being able to infer that a participant has been allocated to the surfactant arm of the trial. The randomising person, person drawing up the surfactant or air placebo and a second person checking the dose will be unblinded. Due to the transient effects and back-tracking it is likely that the Usual Care Nurse (UCN) will become unblinded, and we therefore recommend that if possible the UCN draws up the surfactant or acts as the witness to the drawing up, to minimise the number of people unblinded. Please see figure 2 for an intervention flowchart showing which staff/steps are blinded and unblinded.

Staff who are unblinded due to their involvement or believe themselves to have become unblinded for any reason are strongly discouraged from discussing this with other members of the team, unless the effect noted is causing an adverse event that requires action. Any staff member who believes themselves to have become unblinded must excuse themselves from any decision making regarding the weaning and extubation of the infant. The need to maintain blinding will be emphasised during all Site Training Visits.

IRAS 220853 Page **33** of **87**

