8.1.1 Immediately prior to administration

A limited physical examination, with minimal handling, must be undertaken in the two hours prior to each administration of the trial intervention (as per Section 8.5.1).

Prior to intervention and in a drug room away from usual staff, the study respiratory physiotherapist, research nurse or other delegated, unblinded staff member will:

- Draw up a dose of poractant alfa or an equal volume of air as placebo according to the random allocation into a syringe
- Ensure a second person is present to witness this process and check the dose volume
- Cover the syringe with an opaque paper shield to maintain blinding of other staff and parents
- Take the syringe to the bedside, along with syringes of sterile 0.9% sodium chloride for tracheal toilet and the BAL sampling set.

Infants in both the treatment and placebo arms of the trial will have 0.9% sodium chloride "normal saline" tracheal toilet and 0.9% sodium chloride BAL immediately prior to administration of the intervention. Both can cause immediate transient desaturation, need for increased sedation but also and more often rapid improvement in gas exchange when obstructing secretions are removed. Tracheal toilet and BAL can also lead to creamy white secretions appearing in the endotracheal tube, and this will be observed in both treatment and placebo groups.

Staff should remind parents, if present, of the purpose of the imminent study procedure and give them the opportunity to remain or leave as they choose. The usual care nurse will remain to care for the participant and assist as required.

Tracheal toilet is usually required for babies with bronchiolitis and will be done as recommended in the SPC before administration of poractant alfa. BAL sampling with 0.9% sodium chloride (2x1mL/kg) will be done if scheduled (section 8.2). Both tracheal toilet and BAL sampling is done by catheter access to the trachea; either via the endotracheal suction port without disconnecting the

IRAS 220853 Page **34** of **87**

infant from the ventilator or by disconnecting the infant from the ventilator and performing hand bagging while a side-port with one-way valve are utilised for the toilet and BAL.

The use of muscle relaxant prior to tracheal toilet, BAL and or administration of the intervention is at clinical discretion.

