11.2 Method of Randomisation

Participants will be randomised to receive either poractant alfa or air placebo in a 1:1 ratio. The randomisation list will be generated by an independent statistician at the CTRC who is not otherwise involved in the BESS trial. Randomisation lists will be computer-generated using block randomisation with random variable block length, stratified by site and duration of ventilation (<24hrs and >=24hrs) prior to randomisation.

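### Unblinded site staff can view every earlier allocation and are not barred from seeking consent or influencing when an infant is randomised, so the next allocation can be guessed better than chance

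*Protocol*

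**What the plan says.** - **Access.** Protocol 7.3 allows unblinded, delegated site staff to log in whenever they wish and "view the allocations of each participant to ensure continuity between shifts". No limit by date, shift or dosing status is given.
- **Who is unblinded.** Protocol 7.4: "The randomising person, person drawing up the surfactant or air placebo and a second person checking the dose will be unblinded". In Protocol 8.1.1 the task of drawing up the dose falls to a list that begins "the study respiratory physiotherapist, research nurse or other delegated, unblinded staff member will".
- **Who may recruit.** Protocol 7.2.1: "Consent will be sought by any appropriately trained and delegated medical staff and where local site policy allows, research nurses or respiratory physiotherapists".
- **Timing.** The same section leaves it to the site research team "to judge when is most appropriate to approach parents about trial participation". Protocol 7.3 sets the outer limit: "Randomisation must be completed within 48 hours of intubation". The 24 h stratum boundary lies inside that window.
- **Lists.** Protocol 11.2 specifies "block randomisation with random variable block length, stratified by site and duration of ventilation" (under 24 h, or 24 h and over). Block sizes are not given.
- **Restriction on unblinded staff.** Protocol 7.4 and 8.1.4 exclude them from weaning and extubation decisions. Neither section mentions screening, consent or the timing of randomisation.

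**The concern.** Allocation concealment protects against selection bias only while the person who decides whether and when to enrol cannot anticipate the next assignment. The web system hides the current entry until consent and eligibility are confirmed. In a short blocked list, however, the past entries carry information about the next one, and the protocol makes those entries visible to people who may also recruit.

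A motive is plausible: Protocol 3.3 notes that surfactant is already used as rescue treatment in some of the most severe cases. A recruiter who wants a sicker infant in one arm could approach, wait or hold back according to a guess. The arms could then differ in severity at entry, and duration of ventilation would be directly affected.

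The protocol recognises that knowledge of allocation can bias decisions after randomisation and guards against it there. It has no matching rule for decisions before randomisation. The access is also wider than its stated reason, because continuity between shifts concerns only infants still being dosed.

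**Working it through.** **1. Inputs.** Total 284 (Protocol 11.3), about 14 sites (Protocol 5), two ventilation strata and 1:1 allocation (Protocol 7.3). The plan states no predictability figure. Its total reproduces: 134 / 0.95 = 141.05, rounded up to 142 per group, and 2 × 142 = 284. Nothing below changes it.

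**2. List length.** 284 / (14 × 2) = 10.1, so about 10 infants per list.

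**3. Guessing rule.** The guesser sees all earlier entries of the list in order and names the more probable arm. Block sizes are an assumption: each set below is drawn with equal probability. The second infant in a list can be checked by hand. After one entry, a block of size b gives the opposite arm next with probability (b/2)/(b − 1).

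- Sizes {2,4}: (1 + 2/3)/2 = 0.83
- Sizes {4,6}: (2/3 + 3/5)/2 = 0.63
- Sizes {4,6,8}: (2/3 + 3/5 + 4/7)/3 = 0.61

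**4. Average over 10 infants (simulation; no information = 50%).** The last column is the chance of the wanted arm if the recruiter could always draw from whichever of two independent lists looks more favourable, that is, the mean of max(p₁, p₂).

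| Block sizes | Correct guess | Next entry certain | Wanted arm, free choice of list |
|---|---|---|---|
| {2,4} | 71.5% | 9.4% | 65.8% |
| {4,6} | 68.1% | 5.8% | 63.4% |
| {2,4,6} | 68.9% | 3.2% | 64.2% |
| {4,6,8} | 66.0% | 2.3% | 61.8% |
| fixed 4 (comparison) | 68.3% | 26.7% | 64.4% |

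Exact enumeration of the four variable-block rows agrees to about 0.2 percentage points. Random block length therefore removes most of the certainty but little of the better-than-chance guessing.

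**5. Limited choice of list.** If the choice is truly open for a share s of infants, the chance of the wanted arm is 0.5 + s × (ceiling − 0.5). The documents give no value for s.

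- s = 0.10: 0.5 + 0.10 × 0.118 = 51.2%, to 0.5 + 0.10 × 0.158 = 51.6%
- s = 0.25: 0.5 + 0.25 × 0.118 = 53.0%, to 0.5 + 0.25 × 0.158 = 54.0%
- s = 0.50: 0.5 + 0.50 × 0.118 = 55.9%, to 0.5 + 0.50 × 0.158 = 57.9%

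**6. Partial history.** If the guesser knows only a third of the earlier entries (an assumption), correct guesses fall to about 55% across the four variable-block sets. This indicates what narrowing the log-in view could gain.

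**The case against.** - **Overlap of roles is inferred from job titles.** Protocol 7.2.1 and 8.1.1 name categories of staff and do not say that one person does both. Protocol 7.4 limits unblinding to a few agreed people and tries to keep the number small. Figure 2, which shows who is blinded at each step, is not reproduced in the text available. This stands: the overlap is allowed, not demonstrated.
- **Staff do not control the 24 h boundary.** A reader might infer that the recruiter can pick either list. Intubation fixes the boundary. Staff can only wait past it, and only for infants identified before 24 h. They also risk the 48 h limit or a decision to wean, and depend on when the parent decides. This stands, and it makes 62–66% a ceiling.
- **The guessing rate needs full information.** Protocol 7.3 does not say that the screen shows order or stratum. This also stands, so 66–72% is the full-history case.
- **Safeguards exist.** A doctor must confirm eligibility, screening logs record reasons for non-inclusion (both Protocol 7.1), and the Trial Management Group monitors screening, consent and randomisation rates (Protocol 14.5). These help, but the doctor need not be unaware of earlier allocations.
- **Severity can be adjusted for.** Blood gas and ventilator data are taken before the first dose (Protocol 8.3), so measured imbalance is not beyond repair. This stands for measured severity only. The primary models in SAP 17.4.1.2 contain no severity index: the t-test is unadjusted, and the mixed model uses ventilation stratum, sex, age and site.
- **Version.** The protocol reviewed has an amendment log ending at version 2.0, while the SAP cites 3.0 and 6.0. Whether 7.3 was later changed cannot be checked here.

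**Conclusion.** The gap is real but moderate. The protocol permits one person to see earlier allocations, seek consent and influence when randomisation occurs. With about 10 infants per list, full sight of the ordered history and strata gives about 66–72% correct guesses against 50%, under assumed block sizes of 2 to 8, with certainty in only about 2–9% of cases. Delay past 24 h could add some influence over the list used: at most 62–66% for the wanted arm, and about 53–58% if the option is open for a quarter to a half of infants.

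A reader might go further and conclude that concealment has failed, that staff can choose the arm, or that no analysis could deal with the resulting imbalance. The documents support none of these. They show an opportunity and no instance of its use; the guess is probabilistic; and measured baseline severity can be adjusted for, while unmeasured severity cannot.

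**What to change.** In Protocol 7.3, restrict the allocation view to infants still within their own dosing period as scheduled in Protocol 8.1. This fully serves the stated purpose of continuity between shifts. Add that, where existing staffing allows, staff with allocation access should not seek consent or decide the timing of randomisation at that site.

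The first change is a permission setting in the randomisation system. The second is a delegation-log rule. It is worded as conditional because randomisation runs around the clock, and strict separation of roles could need extra staff on some shifts. Sample size, dosing and clinical care are unaffected.

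The risk is reduced, not removed. Randomising staff still know their own cases, accountability logs link vials to patients (Protocol 9.2.6), and Protocol 7.4 accepts that some allocations will be inferred at the bedside.
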